Design:	Prospective, multicentre, randomised, open-label, cluster crossover, registry-embedded trial
Overall aim:	To compare two approaches to accepted stress ulcer prophylaxis treatment regimens
Primary outcome:	In-hospital all-cause mortality (censored at 90 days)
Secondary outcome:	
 a) proportion of patients with clinically significant upper gastrointestinal bleeding b) proportion of patients with Clostridium difficile infection c) duration of mechanical ventilation d) duration of ICU stay e) duration of hospital stay
Target accrual:	9,300 adults
Inclusion criteria:	
 • >18 years old • Admitted to a participating ICU • Invasively mechanically ventilated with 24 hours of ICU admission
Exclusion criteria:	
 • ICU admission diagnosis of upper gastrointestinal bleeding
Duration of recruitment:	12 months
Duration of participant follow-up:	ICU discharge
Definition of end of trial:	Last participant discharge

1. Background

Around 80% of mechanically ventilated adults in Australian and New Zealand intensive care units (ICUs) are prescribed stress ulcer prophylaxis¹ (SUP). Most patients receive a proton pump inhibitor (PPI) but a sizable minority receive a histamine-2 receptor blocker (H₂RB)^{1,2}. The rationale for using SUP is to prevent morbidity and mortality that might be attributable to occurrence of clinically significant upper gastrointestinal (GI) bleeding. Such bleeding occurs in 2.6% (95%CI, 1.6-3.6 %) of ICU patients in contemporary clinical practice³. In a recent systematic review and meta-analysis comparing PPIs with H₂RBs for ulcer prophylaxis in the ICU, PPIs resulted in a significantly lower risk of overt bleeding than H₂RBs⁴. However, using PPIs instead of H₂RBs also appears to be associated with an increased risk of developing nosocomial pneumonia⁵⁻⁷ and may also be associated with an increased risk of *Clostridium difficile* infection⁵.

Despite the fact that SUP is administered to millions of ICU patients around the world every year, it is uncertain which type is preferable. Moreover, current variability of practice in relation to choice of SUP is largely dependent on clinician preference or unit policy¹. Clinical trials of adequate size to determine whether PPIs or H₂RBs are best for have not been performed and are a high priority given the widespread use of these medicines. Here we outline the protocol for the Proton Pump Inhibitors vs. Histamine-2 Receptor Blockers for Ulcer Prophylaxis Therapy in the Intensive Care Unit (PEPTIC) study.

2. Trial Design

The PEPTIC study is a multicentre, randomised, open-label, cluster crossover, registry-embedded trial in mechanically-ventilated adults implemented at the level of the ICU.

2.1 Efficient design

The design of the PEPTIC study combines two novel trial methodologies: cluster crossover randomisation⁸ and collection of outcome data from existing data sources⁹. This design offers the dual prospect of generating the statistical power necessary to evaluate candidate interventions with small effect sizes and of being much cheaper than a conventional randomised trial by using data that are already collected for other purposes.

The cluster crossover design will randomise entire ICUs rather than individual patients. Each ICU will define a cluster and each ICU will crossover to use both of the treatment approaches being tested by the end of the study. Where possible, existing registry data sources will be used to collect baseline, intervention, and outcome data for the patients admitted to the study ICUs during the trial. Recent academic discourse has highlighted the potential for 'big data' to advance medical knowledge¹⁰ but performing a large scale randomised trial relying on multiple existing data sources is a new innovation in clinical research. In addition to being innovative, we submit that this may be the optimal trial design for testing ubiquitous ICU interventions where the necessary data are already being collected for quality assurance and other purposes, and where clinical equipoise exists over two accepted treatment regimens.

2.2 Setting

In this protocol, 'site' refers to the 12 general intensive care units where the trial will be conducted.

2.2.1 Site requirements

- Active participation in the CMP
- Compliance with responsibilities as stated in the PEPTIC Study Site Agreement;
- Compliance with all requirements of the study protocol;
- Compliance with the research governance framework for health and social care and International Conference on Harmonization Guidelines on Good Clinical Practice (ICH-GCP)

2.2.2 Site responsibilities

- Identify two local joint Principal Investigators (PIs) – one critical care consultant and one critical care nurse – to lead the study locally
- Identify a PEPTIC Research Nurse or coordinator responsible for local coordination
- Agree to incorporate the PEPTIC study into routine intensive care clinical practice, ensuring enrolment of all eligible patients
- Agree to ensure adherence with trial protocol and data collection requirements

2.2.3 Site initiation and activation

Prior to a site being activated, the following must be in place:

- a completed site initiation visit (in person or by teleconference)
- all relevant institutional approvals (e.g. confirmation of capacity and capability);
- a fully signed PEPTIC Study Site Agreement; and
- a completed Delegation Log

Once it has been confirmed that all documentation is in place, a site activation e-mail will be issued to the joint- PIs, at which point, the site may start to recruit patients. Once the site has been activated, the PIs are responsible for ensuring:

- adherence to the most recent approved version of the protocol;
- training of relevant site staff in accordance with the trial protocol and GCP requirements;
- appropriate recruitment and care for patients in the study; and
- timely data collection, entry and validation

All local staff involved in the conduct of the trial must be listed on the Delegation Log, highlighting their delegated duties. The log should be copied and sent to the ICNARC PEPTIC team whenever changes are made.

2.3 Population

To be eligible, patients must meet all of the inclusion criteria, and none of the exclusion criteria:

2.3.1 Inclusion criteria

- age 18 years or older
- admitted to a participating ICU
- invasively mechanically ventilated with 24 hours of ICU admission

2.3.2 Exclusion criteria

- ICU admission diagnosis of upper GI bleeding

2.3.3 Co-enrolment

The PEPTIC trial investigators will consider co-enrolment of trial participants onto other interventional studies where there is no possible conflict with the PEPTIC trial aims. Co-enrolment will be on a case-by-case basis.

2.3.4 Screening

Screening of individual patients will not be performed, all eligible patients will be enrolled and identified from the CMP. Screening logs will record any patients that are eligible but not enrolled.

2.4 Consent and randomisation

2.4.1 Opt-out consent

Patients involved in PEPTIC will be receiving a standard treatment which they would receive regardless of the unit's participation in the study. In this manner, the study treatment represents usual care for which specific consent would not usually be sought.

Furthermore, by definition, critically ill patients in ICU are in a serious condition due to their illness and require support for one or more organ functions. Mechanical ventilation is an invasive procedure, often used in parallel with sedative and analgesic drugs. These factors restrict the patient's capacity to consent. It would not be possible to conduct critical care research if confined to patients able to consent.

For these reasons, specific patient consent will not be required. No patient identifiable data will be collected centrally during the course of the PEPTIC study. Patients will be actively approached at an appropriate time by site staff with an information leaflet, which highlights how patients can opt-out of data collection. Posters will also be displayed around participating ICUs, giving patients and their relatives the opportunity to opt out.

2.4.2 Process for opt-out

Patients who choose to opt-out will be noted on a specific log, and their data will not be extracted from the CMP. They will continue to receive SUP treatment, as this forms a standard part of their care.

2.4.3 Randomisation

Study ICUs will be randomised at a minimum of a four at a time in a 1:1 ratio to either:

- Open-label use of PPI
- Open-label use of H₂RB

At the end of the first six-month study period, the sites will crossover for a second six-month period.

2.5 Procedures

2.5.1 Commencing treatment

Units will administer either PPI or H₂RB to all eligible patients according to the unit randomisation. Clinicians are free to use the alternative treatment in situations where that is clearly preferable. Patients who are usually taking a PPI or an H₂RB will switch to the assigned treatment strategy for the duration of their ICU stay unless the treating clinician believes that this is inappropriate.

2.5.2 During treatment

If overt upper GI bleeding occurs, then a PPI will be administered irrespective of treatment allocation. This is in accordance with standard clinical practice.

2.5.3 End of treatment

The decision to discontinue SUP lies with the treating clinician. The duration of the study treatment will be until ICU discharge, death, or until SUP usage is no longer indicated.

All other care will be determined by the clinical team primarily responsible for the participant's care.

2.6 Outcomes

2.6.1 Primary outcomes

- In-hospital all-cause mortality, censored at 90 days

2.6.2 Secondary outcomes

- Proportion of patients with clinically significant upper GI bleeding
- Proportion of patients with *Clostridium difficile* infection
- Duration of mechanical ventilation (for ICUs where this information is available from an existing database)
- ICU length of stay
- Hospital length of stay

2.7 Data collection

To maximise the efficiency of the trial design, data collected for PEPTIC is nested in the CMP. Data extracted from the CMP for participating patients will include:

- Demographics (age, gender)
- Admission (type, source)
- Chronic co-morbidities
- Admission diagnosis
- Illness severity
- Length of stay (ICU, hospital)
- Duration of mechanical ventilation
- In-hospital mortality

Additional patient data collected at each site by research nurses or coordinators will be limited to:

- Patients who develop clinically significant upper GI bleeding
- Patients who develop *Colostridium difficile*
- Details of SUP administered to patients from electronic prescribing records where available, or a monthly audit of the unit where unavailable

This data will be collected on to Excel spreadsheets with no patient identifiable information recorded.

3. Trial closure

3.1 End of trial

The end of the trial will be when the final patient recruited is discharged from the ICU at which point the 'declaration of end of trial' form will be submitted to the REC by ICNARC CTU.

3.2 Archiving trial documents

At the end of the trial, ICNARC CTU will securely archive all centrally held trial-related documents for a minimum of five years, in accordance with ICH-GCP guidelines. Arrangements for confidential destruction of all documents will then be made. The site PIs will be responsible for archiving any trial-related documents, although this is expected to be minimal. Essential documents are those which enable both the conduct of the study and the quality of the data produced to be evaluated and to show whether the site complied with the principles of ICH-GCP and other regulatory requirements.

Guidance on archiving will be provided in the study-specific SOP. All archived documents, both locally and centrally, should be available for inspection upon request.

4. Statistical analysis

4.1 Sample size calculation

With 40 ICUs (international) and assuming a baseline mortality of 15%, our study will have 80% power to detect a 2.7% absolute difference in in-hospital mortality. This sample size is based on an average of 310 admissions per site in each 6-month study period. It incorporates a within-cluster-within-period correlation of 0.035 and within-cluster-between-period correlation of 0.025.

4.2 Statistical analysis plan

Analyses will be conducted on an intention-to-treat basis. Analyses of the primary end point will involve ICU (cluster) summary measures obtained by aggregating the primary endpoint to a rate per ICU per time period and calculating the difference in event rates between the first and second periods for each ICU. These differences will then be entered as the dependent variable into an unweighted linear regression with randomised sequence as the independent variable¹⁴, from which the coefficient of the randomised sequence is then the estimated PPI versus H₂RB difference. Such analyses appropriately control for all clustering effects within ICU and common secular time trends across ICUs. Uncertainty concerning treatment effects will be estimated using standard 95% confidence intervals. For secondary outcomes on a binary scale the same methods will apply, and for outcomes on a continuous scale previously described linear mixed model methods will be applied¹⁵. Sensitivity analyses will be performed for the impact of patients with missing outcome data using multiple imputation methods.

Pre-specified subgroup pairs will be patients who are admitted to the ICU following cardiac surgery vs. patients admitted for any other reason and emergency vs. elective admissions. We will perform the analyses described above for the primary and secondary outcome variables separately for each subgroup. Each analysis will be accompanied by a test for interaction between treatment and subgroup to ascertain whether treatment effect differs significantly between subgroups. Analyses will be performed using the Stata software package (StataCorp, Texas, USA).

5. Trial oversight and ethical compliance

The chief investigator ([name]) will take overall responsibility for delivery of PEPTIC and oversee progress against timelines/milestones.

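### The primary analysis is fixed as unadjusted although prognostic covariates are already in the registry extract, so precision of uncertain size is given up

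*Protocol*

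**What the plan says.** Protocol Section 2.6.1 defines the primary outcome as "In-hospital all-cause mortality, censored at 90 days". Section 4.2 sets out its analysis in full. Deaths are summarised by "aggregating the primary endpoint to a rate per ICU per time period", each ICU's two rates are subtracted, and the differences go into an unweighted linear regression whose only regressor is randomised sequence. The section says this handles clustering within ICU and time trends common to all ICUs. It does not mention case mix. The only sensitivity analysis it names is multiple imputation for missing outcomes.

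Section 2.7 lists what is taken from the UK registry (the CMP) for each patient: age and gender, admission type and source, chronic comorbidity, admission diagnosis and "Illness severity", together with in-hospital death.

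Section 4.1 claims "80% power to detect a 2.7% absolute difference in in-hospital mortality" with 40 ICUs, a baseline mortality of 15%, "an average of 310 admissions per site in each 6-month study period", and a "within-cluster-within-period correlation of 0.035 and within-cluster-between-period correlation of 0.025". It does not say where the correlations come from, whether they are crude or risk-adjusted, or what produces the gap between them.

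**The concern.** Each ICU is its own control, but the two six-month periods contain different patients. What is stable about an ICU, including its usual case mix, cancels in the within-ICU difference. What does not cancel is any change in that ICU between its two periods, including a change in who is admitted. A time trend shared by all ICUs is removed by the sequence regression; an ICU-specific shift is not.

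The admitted population is mixed. The protocol's own subgroups separate cardiac surgery from other admissions, and elective from emergency admissions. A modest shift in mix could therefore move a crude death rate. With 40 randomised units, such shifts need not balance between sequences.

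The stake is efficiency. If part of the ICU-by-period variation can be explained by covariates already held, the trial could detect a smaller difference with the same ICUs and patients. Adjustment chosen after an imbalance has been seen would carry less weight than adjustment fixed beforehand.

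**Working it through.** **Inputs (Section 4.1).** K = 40 ICUs; m = 310 per ICU-period; baseline risk 0.15; within-period correlation 0.035; between-period correlation 0.025. The significance level is not stated for the sample size; two-sided 5% is assumed, in line with the 95% intervals in Section 4.2. Cluster sizes are taken as equal.

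**Formula.** For the unweighted within-ICU comparison,

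Var = (2 × p(1 − p) / K) × [(1 − 0.035)/m + (0.035 − 0.025)].

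**Step 1: reproduce the stated power.** The bracket is 0.965/310 + 0.010 = 0.00311 + 0.01000 = 0.01311.

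- Risks of 15% and 17.7%: mean p(1 − p) = (0.1275 + 0.1457)/2 = 0.1366. SE = √(2 × 0.1366 × 0.01311 / 40) = 0.95 points. Power for 2.7 points is 81.4% (normal) or 79.4% (t, 38 df). The detectable difference at 80% power is 2.65 or 2.72 points.
- Variance at 15% in both arms: p(1 − p) = 0.1275, SE = 0.914 points. Power is 84.0% or 82.1%, and the detectable difference is 2.56 or 2.63 points.

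The protocol's 80% for 2.7 points is therefore reproduced.

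**Step 2: split the variance.**

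- Patient sampling: 0.00311/0.01311 = 24%, an SD of √(0.1275 × 0.00311) = 2.0 points per ICU-period.
- ICU-by-period variation: 0.01000/0.01311 = 76%, an SD of √(0.1275 × 0.010) = 3.6 points per ICU-period.
- Stable between-ICU variation (correlation 0.025, SD 5.6 points) cancels in the difference.

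**Step 3: what more patients would buy.** As m grows without limit, the first term vanishes. SE becomes √(2 × 0.1275 × 0.010 / 40) = 0.798 points, and the detectable difference is 2.24 (normal) or 2.30 points (t). Against 2.56 and 2.63, this is a small gain for unlimited recruitment within the same ICUs.

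**Step 4: what adjustment might buy.** Each term is multiplied by one minus the share that covariates explain. The documents give no such share, so the values below are assumed. The variance is at 15% in both arms. The detectable difference is (2.024 + 0.851) × SE, and power uses the noncentral t with 38 df and noncentrality 2.7/SE.

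| Explained, patient level | Explained, ICU-by-period | Bracket | SE (points) | Detectable difference (points) | Power for 2.7 points |
|---|---|---|---|---|---|
| 0% | 0% | 0.01311 | 0.914 | 2.63 | 82% |
| 25% | 0% | 0.01233 | 0.887 | 2.55 | 84% |
| 25% | 25% | 0.00983 | 0.792 | 2.28 | 91% |
| 25% | 50% | 0.00733 | 0.684 | 1.97 | 97% |

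The first adjusted row cuts total variance by 6%, the second by 25% and the third by 44%. Nearly all of the gain depends on the ICU-by-period column.

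**The case against.** The strongest reply is that nothing here is wrong. Regressing ICU-level differences on randomised sequence is valid under randomisation. Chance shifts in case mix are random error that the confidence interval already covers, and the stated power already carries the ICU-by-period variance. That stands: the crude estimate is not biased and Section 4.1 is not miscalculated.

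A reader might infer from the 76% that case mix dominates the variance. The documents do not support this. Section 4.1 gives two correlations and no cause for the gap. Changes in staffing, practice or discharge policy could produce it as well, and if the correlations are already risk-adjusted, it would not be case mix as adjusted for. If covariates explain none of that component, the gain is only the 2.55-point row.

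Two practical objections also stand in part. Section 2.7 describes the UK registry only. Section 2.2 gives 12 sites under this protocol against 40 ICUs internationally, and nothing shows that the other datasets hold the same fields. The timing of the severity score is not given either, so in an open-label trial it may be measured after prophylaxis has begun.

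Finally, a statistical analysis plan not shown here may add an adjusted secondary analysis. That would meet the point if it is pre-specified and reported alongside the crude result. It does not remove the point altogether, because Section 4.2 names the summary measure, the regressor and the weighting of the primary analysis rather than leaving them open.

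**Conclusion.** The point holds as an inexpensive improvement, not as an error. The protocol fixes a crude primary analysis while prognostic covariates are already being extracted, at least in the UK. About 76% of the planned variance is of a kind that recruiting more patients per ICU cannot reduce. That share follows from the protocol's own correlations.

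The size of the benefit does not follow from the documents. It runs from slight (2.63 to 2.55 points) to substantial (1.97 points), depending on how much ICU-by-period variation is a change in measured case mix. These figures rest on equal cluster sizes, two-sided 5%, variance at 15% in both arms, and assumed explained shares. The 2.63-point starting value is a little below the protocol's 2.7 because of that variance convention; it does not show a discrepancy.

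**What to change.** Pre-specify a two-stage adjusted analysis in Section 4.2 or in the statistical analysis plan:

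1. Confirm that each national dataset holds age, sex, admission type and source, comorbidity and admission diagnosis.
2. Within each national dataset, fit a patient-level logistic model for in-hospital death on those covariates, leaving treatment out.
3. For each ICU-period, compute (observed − expected deaths)/n.
4. Take the period difference within each ICU and enter it into the same sequence regression, which keeps the absolute-difference scale.

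Make this the primary estimate or a pre-specified co-reported one, and report the crude analysis beside it in either case. Use severity scores that may be measured after treatment starts only in a sensitivity analysis.

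The cost is a few lines of text, modest programming, a rule for missing covariates, and the check on fields in step 1. No additional recruitment is needed.

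### The primary regression fits one period effect for all ICUs, although ICUs are randomised in batches and pooled internationally; a region or batch term would be a cheap gain in precision

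*Protocol*

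**What the plan says.** Section 2.4.3 of the protocol sets the allocation: "Study ICUs will be randomised at a minimum of a four at a time in a 1:1 ratio". Each ICU then runs two six-month periods, one per strategy.

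Section 4.1 plans for the whole international trial: "With 40 ICUs (international) and assuming a baseline mortality of 15%, our study will have 80% power to detect a 2.7% absolute difference". Section 2.2 places 12 ICUs under this UK protocol, and section 5.2 says that the UK data go to New Zealand to be analysed together with the other countries' data.

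Section 4.2 fixes the primary model. Each ICU contributes one number, the difference between its two period mortality rates. These differences enter an unweighted linear regression whose only explanatory term is randomised sequence. The section then states: "Such analyses appropriately control for all clustering effects within ICU and common secular time trends across ICUs". It names no term for batch, country, region or calendar time.

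**The concern.** In a regression of period differences on sequence, the intercept is the period effect, and here every ICU shares it. That suits a trial in which all ICUs move through the same calendar time under the same conditions.

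Two features make this doubtful. First, a six-month period is half a year, so period and season coincide within an ICU. If ICUs in opposite hemispheres start together, period 1 is the winter half for some and the summer half for others, and their seasonal contrasts have opposite signs. Second, ICUs are randomised in batches, and section 2.2.3 lets a site recruit once it is activated, with no common calendar start stated.

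Any part of the period difference that varies by region or batch goes into the residual. Because sequence is allocated 1:1 within batch, this does not bias the treatment estimate. It does inflate the reported standard error, so confidence intervals are wider than they need be and power is lost. Section 4.1 leaves no spare power.

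**Working it through.** **Inputs.** From section 4.1: 40 ICUs, baseline mortality 15%, a 2.7-point difference, m = 310 per ICU per period, and "within-cluster-within-period correlation of 0.035 and within-cluster-between-period correlation of 0.025". Two-sided 5% is assumed, in line with the 95% intervals of section 4.2, because section 4.1 gives no alpha.

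**Reproducing the planned power**
- Design effect = 1 + (310 − 1) × 0.035 − 310 × 0.025 = 4.065.
- Variance of one ICU's period difference, 15% vs 17.7%: V = (0.15 × 0.85 + 0.177 × 0.823) / 310 × 4.065 = 0.003582 (SD 5.99 points).
- The treatment effect is half the difference between the two sequences' mean period differences, so SE = √(V/40) = 0.00946.
- Power = 81.4% (normal) or 79.4% (t, 38 df). The stated 80% reproduces.

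**Adding a period contrast that is not common.** Let a share f of ICUs have period difference +s and the rest −s. This adds 4f(1 − f)s² to V. The protocol gives no value for s, so s is an assumption shown as a range. For f, 0.3 corresponds to 12 of 40 ICUs, and 0.5 is the split that adds most variance.

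| s (points) | Added variance, f = 0.3 to 0.5 | Power of planned model (t, 38 df) |
|---|---|---|
| 0 | 0% | 79.4% |
| 0.5 | 0.6 to 0.7% | 79.2 to 79.1% |
| 1 | 2.3 to 2.8% | 78.5 to 78.3% |
| 2 | 9.4 to 11.2% | 75.8 to 75.1% |
| 3 | 21.1 to 25.1% | 71.5 to 70.0% |

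For example, s = 2 and f = 0.5 adds 0.02² = 0.0004, and 0.0004/0.003582 = 11.2%. The standard error then rises by √1.112, about 5%.

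**With adjustment.** If the contrast lies between regions, a region term leaves 40 − 3 = 37 df and gives 79.3% whatever s is. Batches of at least four mean at most 40/4 = 10 batches; a term for each leaves 40 − 11 = 29 df and gives 78.7%. Against the table, batch terms lose slightly at s = 0.5 and gain 0.2 to 0.4 points at s = 1.

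**Simulation** (ten batches of four, sequence balanced in each, half the batches at +s and half at −s):
- The estimate is unbiased.
- Type I error of the planned model falls to about 4.7%, 3.7% and 2.8% at s = 1, 2 and 3.
- Power is 75.9% at s = 2 and 71.5% at s = 3. The formula gives 75.1% and 70.0% for the same split, so it overstates the loss by 0.8 and 1.5 points. It treats the contrast as random noise, whereas balance within batch keeps the contrast out of the estimate.

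**The case against.** The strongest reply is that nothing in section 4.2 is wrong. A reader might infer that the quoted sentence claims control that the model lacks. It does not: it speaks of trends common to the ICUs, and the intercept does remove those.

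A reader might also infer that the protocol describes staggered batches spread over both hemispheres. It does not say so. The countries of the 40 ICUs are not listed; southern-hemisphere ICUs are inferred from the analysis centre in New Zealand (section 5.2) and from the Australian and New Zealand endorsement and New Zealand funding (section 6.2). The batch rule stands in a UK protocol for 12 ICUs, and ten batches of four is the smallest batch size allowed, not a stated fact. The summary gives 12 months of recruitment, which two six-month periods fill, so there is little room for staggered starts among the UK sites.

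The contrast itself is assumed. Two points is 13% of a 15% baseline (2/15), and the equal split is the least favourable.

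Some of it may also be allowed for already. The gap between the two correlations is an ICU-by-period variance of 0.01 × 0.1275 = 0.001275 (SD about 3.6 points). In a period difference it is 2 × 0.001275 = 0.00255 (SD about 5.0 points). At 15% in both periods V is 0.00334, so this component is about 76% of it. If the correlations came from data with seasonal variation, part of the loss is inside the planned 80%, and adjustment would gain on the plan and not repair a shortfall.

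All of this stands, and it limits the point. What remains is that the protocol itself fixes a sequence-only model, that this model ignores the groups used to randomise, and that allowing for them costs very little.

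**Conclusion.** The point holds as a low-cost improvement in precision. If period effects differ by region or batch, the planned model puts that variation in the residual. The estimate remains unbiased, the standard error is too large and the test conservative. By the formula, the loss is about 1 point of power at an assumed contrast of 1 percentage point, about 4 at 2 points and 8 to 9 at 3 points; with balance within batches it is somewhat smaller. Below about 1 point it is negligible.

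This rests on the section 4.1 inputs, a two-sided 5% level, an assumed seasonal contrast, and an inferred spread of ICUs over both hemispheres. The documents do not support a stronger conclusion that the primary result would be biased, that false positives would increase, or that the trial is shown to be underpowered.

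**What to change.** Pre-specify one further term in the ICU-level regression of period differences, before outcome data are seen:

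- **Preferred: region (hemisphere) or start season.** It uses 1 of 38 df and costs about 0.1 point of power if there is no contrast (79.4% to 79.3%). It recovers the loss to the extent that the contrast follows that grouping.
- **Alternative: randomisation batch as a fixed factor.** This matches the analysis to the allocation and also covers differences in start date. It uses up to 9 df and costs about 0.7 point if there is no contrast (79.4% to 78.7%), so it gains only once the contrast is about 1 point or more.

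Amend the sentence in section 4.2 to say that period effects are controlled within region or batch, whichever is chosen. The cost is one covariate and one sentence; no data beyond each ICU's location, start date and batch are needed.
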